This study manipulates e-cigarette nicotine flux systematically, testing the hypothesis that abuse liability will be related directly to flux among a sample of cigarette smokers. No previous study has manipulated nicotine flux and examined within-group effects, so we could not estimate effect size. Thus, we calculated a sample size to achieve a power of >0.80 with $\alpha <0.05$ and assuming a small effect size (Cohen's $f=0.20$) and moderate repeated measures correlation ($r=0.5$) in a repeated measures ANOVA with nicotine flux as within-subjects factors (N=32; GPower). In Study 2, 40 cigarette users will attend the lab for 5 sessions - no flux, low flux, cigarette-like flux, high flux, and an own brand cigarette control (always session 5). We hypothesize that flux will be positively associated with willingness to pay/work (drug purchase task, progressive ratio task) and willingness to substitute e-cigarettes for own brand cigarettes (cross-product drug purchase task, cross-product progressive ratio task), and inversely to price sensitivity (drug purchase task) for all smokers.

It is possible that we would consent up to 100 participants in order to obtain 40 participants who complete the entire study.

4. * List the study inclusion criteria:

All participants must be healthy (determined by self-report), between the ages of 18-55 (verified by photo ID), willing to provide informed consent, and attend the lab and abstain from tobacco/nicotine as required. Participants must agree to use designated products according to the study protocol.

Participants must use at least 5 cigarettes per day if they are not classified as dual users of inhaled tobacco products.

Participants classified as dual users of inhaled tobacco products must meet at least of two definitions described below:

- at least some day use of cigarettes (≥ 3 days per week at any cigarettes per day frequency) AND
- daily use of another inhaled tobacco product (e.g., e-cigarettes, cigars, pipe)

OR

- daily use of cigarettes (at any cigarettes per day frequency) AND
- at least some day use of another inhaled tobacco product (e.g., e-cigarettes, cigars, pipe; ≥ 3 days per week at any frequency).

Participants must have a 'positive' cotinine cassette result to verify nicotine use.

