Physiological measures. Physiological measures are being collected primarily for participant safety during sessions. HR/BP will be measured and saved electronically using software and equipment that sounds an alarm if safety parameters are exceeded (Model 506, Criticare Systems).

Behavioral measures. Our primary behavioral measures are four behavioral choice tasks (Progressive Ratio Task, Cross Product-Progressive Ratio Task, Drug Purchase Task, and Cross Product-Drug Purchase Task).

The Progressive Ratio Task (PRT) requires participants to click on a button on a computer to earn puffs of the session-specific ECIG or their own brand cigarettes. Ten key presses are required to earn the first puff, and this number is increased by 30% for each subsequent puff. Once the participant declines to press the button for five minutes then the PRT is considered complete. PRT outcome measures are 1) breakpoint PRT (maximum number of key presses completed to earn a puff), 2) number of puffs self-administered, and 3) latency (sec) to initiate key pressing. Data is collected via a software program created using Python. The data file is stored locally, under a username and password protected profile. It is then copied to secure storage locations (such as Ironkey or R-Drive) after each session.

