The Cross Product-Progressive Ratio Task (CP-PRT). The CP-PRT asks the participants to perform work, in the form of key presses for puffs of a condition-specific product or own brand cigarette. Using a concurrent schedule (Audrain-McGovern et al., 2015, 2014; Perkins et al., 1994; Perkins et al., 2002), participants are told that they can switch from working for one product or the other as often as they wish. Participants are instructed to press either a "A" key (condition-specific ECIG) or "L" key (own brand cigarette). Consistent with relative reinforcement paradigms, the reinforcement schedule for the session-specific product remains constant at a fixed ratio FR-25 (25 presses achieved to earn a point) while the reinforcement schedule for the own brand cigarettes increases by 25 space bar presses over 10 trials, such that 25, 50, 75, 100, 125, 150, 175, 200, 225, and 250 presses are required to earn a puff (similar to Audrain-McGovern et al., 2015, 2014; Bickel et al., 2000; Epstein et al., 2007). Participants will be randomized to either receive the earned cigarette or ECIG puffs first. Cross-PRT outcome measures are 1) Breakpoint or the highest trial (out of 10 trials) that was completed for own brand cigarette puffs. Data is collected via a software program created using Python. The data file is stored locally, under a username and password protected profile. It is then copied to secure storage locations (such as Ironkey or R-Drive) after each session.

The Drug Purchase Task (DPT) assesses hypothetical tobacco product purchasing behaviors for the session specific ECIG (assessed at sessions 1-4) and own brand CIG (assessed during the own brand session). The outcomes from the DPT include the breakpoint (highest price participants were willing to pay), elasticity (change in amount purchased as price increases), Omax (highest amount individuals paid in any choice, i.e., maximum value of price*quantity), Pmax (the price associated with Omax), and intensity (amount "purchased" when the price is zero/free). Data is collected via REDCap survey and stored under username/password with specific access per user.

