The Cross Product (CP)-DPT assesses cross-product purchasing behaviors (assessed at sessions 1-4) between session-specific ECIG products offered at a fixed amount and own brand cigarettes offered at varying prices (\$0-20.48). The main outcome for the CP-DPT is cross-price elasticity, or the extent to which purchasing of the session-specific ECIG increases when the price of own brand cigarettes increase. Both the DPT and CP-DPT tasks are programmed to end early if participants report zero consumption for assessed products. Estimated time per measure is <3 min, and each measure will only be completed once per session. Data is collected via REDCap survey and stored under username/password with specific access per user.

Subjective measures. Repeatedly within each condition we will use the Minnesota Nicotine Withdrawal Scale, the

Direct Effects of Nicotine Scale, the Direct Effects of Vaping Scale, the Generalized Labeled Magnitude Scale and the Labeled Hedonic Scale to measure tobacco abstinence symptoms and product assessment before and after each behavioral measure. We will also ask a validation question at the end of each session, "Do you think there was nicotine in the product you used today?". Data is collected via REDCap survey and stored under username/password with specific access per user.

Additional Detail Regarding Product Use. Participants are not expected to consume all of the liquid that is loaded into the ECIG device for each session. Their product exposure will be limited to the 4 test puffs at the beginning of the session and puffs that they may take as part of the PRT (no puff limit provided; self-directed by the participant) and CP-PRT (limited to a maximum of 10 puffs; self-directed by the participant). We do not expect participants to take more than 40 puffs across the entire session/tasks (~3.5 hours) based on our experience with these tasks and ECIG conditions used previously. Of note we have another study in progress with similar task/puff requirements using a similar nicotine concentration liquid with no adverse effects noted among our participants.

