Data analysis. Subjective, physiological, DPT, CP-DPT, PRT, and CP-PRT data will be prepared as reported elsewhere ([name] et al., 2017; Rusted et al., 1998; [name] et al., 2010). Elasticity is estimated using an exponential demand function with nonsystematic DTP data excluded based on two criteria: trend, or whether the participant had a general decrease in consumption from the lowest to highest price; and bounce, or whether a participant reported higher consumption at sequential higher prices (Stein et al., 2015). In general, analysis will involve a mixed (between- and within-subject) ANOVA. Demographic data will be examined to determine if there are significant between-group differences on measures that may be related to study outcomes. Unexpected between group differences will be considered as potential covariates in the primary analysis (see Evans et al., 2006). Statistical analyses may utilize regression, ANOVA, or mixed linear models. Adjustments for sphericity violations and post-hoc testing using Tukey's HSD or planned contrasts with Bonferroni corrections will be used (Keppel, 1991). Based upon the type and amount of missing data, we may use accepted techniques such as multiple imputation (Allison, 2001).

7. * The IRB only reviews research activities, so indicate for each of the study activities described in the question above or in the protocol which activities are:

- Being performed exclusively for research purposes (i.e. they would not otherwise be done apart from this study) **VERSUS.**
- Alterations of routine activities/procedures (e.g. the study is altering the timing, frequency, method, location, amount, etc.) **VERSUS.**
- Being done for other purposes and whose data/results will be used secondarily in the study (e.g. standard medical or psychological tests, routine education practices, quality improvement initiatives, etc.).

See the help text for additional guidance

All of the procedures described above are performed exclusively for research purposes. There are no alterations of routine procedure and no procedures would be performed if these individuals were not taking part in this research study.

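### Four primary tasks yield ten outcomes with no lead outcome and no control across them; under the null, the chance of a false positive could reach about 34% for the flux hypothesis and 10% for substitution.

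*Combined protocol and SAP*

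**What the plan says.** Under Study Procedures, item 6, the behavioral measures text opens: "Our primary behavioral measures are four behavioral choice tasks". It then lists outcomes task by task.

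- **Progressive Ratio Task (PRT), three outcomes:** "PRT outcome measures are 1) breakpoint PRT (maximum number of key presses completed to earn a puff), 2) number of puffs self-administered, and 3) latency".
- **Cross-product PRT (CP-PRT), one outcome:** "Cross-PRT outcome measures are 1) Breakpoint or the highest trial (out of 10 trials) that was completed for own brand cigarette puffs".
- **Drug Purchase Task (DPT), five outcomes:** "The outcomes from the DPT include the breakpoint (highest price participants were willing to pay), elasticity", followed by Omax, Pmax and intensity.
- **Cross-product DPT (CP-DPT), one outcome:** "The main outcome for the CP-DPT is cross-price elasticity". The word main ranks nothing outside that task.

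Study Population, item 3, gives the only alpha for this study, as a "power of >0.80 with $\alpha <0.05$ and assuming a small effect size" "in a repeated measures ANOVA with nicotine flux as within-subjects factors (N=32; GPower"). The same item ties willingness to pay or work to the DPT and PRT, price sensitivity to the DPT, and substitution to the two cross-product tasks.

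On multiplicity, the Data analysis paragraph says that "post-hoc testing using Tukey's HSD or planned contrasts with Bonferroni corrections will be used". It sets no significance level per outcome, and it leaves the model open among regression, ANOVA and mixed linear models.

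**The concern.** The study is sized for one test, but the analysis can produce ten, all of equal standing. The hypotheses are worded by construct and task, not by index. Nothing says which index, or how many, must be positive before a hypothesis counts as supported.

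The Tukey and Bonferroni sentence is most naturally read as covering comparisons between conditions within one outcome. Nothing extends it to the set of outcomes.

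The stated aim is to inform tobacco product regulation. One favourable index among several could be reported as confirming the flux claim, and a reader could not tell how many chances that index had.

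**Working it through.** **1. The plan's own figure.** Inputs from Study Population, item 3: f = 0.20, r = 0.5, alpha 0.05, power above 0.80. For a one-group repeated measures ANOVA with m conditions and sphericity, lambda = f² × N × m / (1 − r), with df = m − 1 and (N − 1)(m − 1).

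- m = 5, N = 32: lambda = 0.04 × 32 × 5 / 0.5 = 12.8, df 4 and 124, power 0.814. The stated N = 32 is reproduced, for one test with five conditions.
- m = 4, N = 32: lambda = 10.24, power 0.753. Four conditions would need N = 36.
- The 40 completers give power 0.852 with m = 4 (lambda 12.8) and 0.902 with m = 5 (lambda 16).

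Nothing in this sizing allows for more than one outcome.

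**2. Count and mapping.** 3 (PRT) + 1 (CP-PRT) + 5 (DPT) + 1 (CP-DPT) = 10. By the sample-size text, flux takes DPT and PRT, 5 + 3 = 8 outcomes. Substitution takes CP-DPT and CP-PRT, 1 + 1 = 2.

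**3. Independent outcomes.** If k outcomes are each tested at 0.05 and flux affects none of them, the chance of at least one rejection is 1 − 0.95^k:

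- flux, k = 8: 33.7%
- substitution, k = 2: 9.75%
- all ten, k = 10: 40.1%

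**4. Correlated outcomes.** The documents give no correlation between outcomes. The values below are assumptions, with one common correlation across all outcomes. They come from simulated repeated-measures F tests (40 participants, four conditions, no flux effect, 20,000 runs per setting or more).

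| Assumed correlation | Flux (8) | Substitution (2) | All ten |
|---|---|---|---|
| 0 (exact) | 34% | 10% | 40% |
| 0.3 | 31% | 9% | 36% |
| 0.5 | 26% | 9% | 31% |
| 0.7 | 20% | 8% | 23% |
| 0.9 | 13% | 7% | 13% to 14% |

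At 0.9 the flux figure depends a little on the test modelled: about 13% for the F test, 12% for a two-sided normal test and 11% for a one-sided normal test at 0.05. Running the flux simulation with five conditions changes little.

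**5. Price of a blanket correction.** Bonferroni over all ten (0.005 each) cuts power at N = 40 from 85% to 57% with four conditions, or from 90% to 67% with five. Restoring 80% power would need N = 57 or N = 49.

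**The case against.** Several points on the other side are sound.

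- **Pooling.** A reader might infer that either hypothesis could be claimed from any of the ten indices, with a 40% error rate for each. The documents do not support that. The sample-size text assigns tasks to hypotheses, so no DPT or PRT index can support substitution. The 40% describes the whole set and neither hypothesis alone.
- **A firm lower limit.** A reader might take some value above 20% as a floor. There is none in the documents. The 23% for all ten requires a correlation of about 0.7, and stronger correlation brings it lower.
- **Overlap.** PRT breakpoint and puff count are nearly one-to-one, because each puff costs 30% more presses than the last. Counting them as one leaves seven flux outcomes: 1 − 0.95^7 = 30.2% if independent. The DPT indices also come from a single purchase task.
- **Alpha.** A reader might infer that the plan orders each outcome tested at 0.05, or promises 5% overall. It does neither. The 0.05 is carried over from the sample-size text. The family for the Bonferroni contrasts is not defined, so limiting it to conditions within an outcome is the natural reading, not a stated rule.
- **Direction.** The hypotheses are directional, while an omnibus F test also rejects for patterns that would not support them. If only a two-sided contrast at 0.05 pointing the right way counted, independence would give 1 − 0.975^8 = 18% for flux and 1 − 0.975^2 = 5% for substitution. The plan does not restrict itself to such a contrast.

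These points lower or qualify the size. None of them supplies a lead outcome, a rule for declaring support, or control across outcomes. Nor do the documents show any intention to select a favourable index; the point is that nothing rules it out.

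**Conclusion.** The concern holds, stated by hypothesis. With eight flux outcomes and two substitution outcomes unranked, the false-positive chance is up to about 34% and 10% with independent outcomes. At an assumed correlation of 0.9 it is roughly 11% to 13% and 7%.

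These figures rest on three assumptions: each outcome is tested at 0.05, flux affects none of the outcomes in the family, and any rejection counts as support. The correlation range is assumed throughout. This should be corrected, but it does not call the design or the sample size into question.

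**What to change.** Before the data are examined, name exactly one lead outcome for each hypothesis, with no alternative left open. Examples are PRT breakpoint for flux and cross-price elasticity for substitution. State the model and comparison that test each one. Then choose one of two schemes:

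- **Separate families:** each lead outcome at 0.05. Neither test waits for the other, but the chance of at least one false claim across the two hypotheses can reach 9.75%.
- **Fixed order:** flux at 0.05, then substitution at 0.05 only if flux is significant. This holds 5% over both. If both effects are real at the planned size and the tests are independent, the chance of claiming substitution falls from about 0.85 to 0.85 × 0.85 = 0.72.

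Report all remaining indices as secondary, with Holm-adjusted p-values within each hypothesis.

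This is a change of wording and needs no extra participants. Each lead outcome keeps about 85% power at N = 40 for the four-condition comparison, or 90% with five conditions where the own-brand session is included (f = 0.20, r = 0.5, sphericity). The cross-product tasks have only four conditions. The cost is that the other indices become supportive; with PRT breakpoint leading, that includes price sensitivity. If the outcome data have already been seen, the ranking must be disclosed as post hoc.

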6. * Since a separate protocol document is not uploaded, describe the proposed research using language understandable to those IRB committee members whose expertise is not scientific. The description must include:

- 1. A statement explaining the study design**
- 2. A detailed description of all the procedures that will be followed to carry out the study, preferably in sequential order, and in sufficient detail that the study's methods could be replicated**
- 3. The schedule and frequency of when and how procedures will be conducted (e.g. in person, online, phone, paper, etc.)**
- 4. A description of all research measures/tests/interventions that will be used, including analyses/tests conducted on specimens/biological samples (if applicable)**

See the help text for additional guidance

Overview. This study involves 40 CIG users who will complete 5, within-subject, laboratory conditions that differ by the product used: 1) 30 W; 0 mg/ml; 2 sec puff, 2) 30 W; 6 mg/ml; 2 sec puff, 3) 30 W; 15 mg/ml; 2 sec puff, 4) 30 W; 30 mg/ml; 2 sec puff, and 5) own brand (tobacco cigarette). The first 4 ECIG conditions will be Latin-square ordered and single blinded such that the participants will not know which condition is administered in each ECIG session. The last condition for all subjects will be their own brand CIG.

Participants. A total of 40 adults (ages 18-55) who currently use CIGs will be enrolled. We will attempt to recruit an equal number of men and women of diverse racial/ethnic backgrounds, although this study is not intended to address gender or race/ethnic differences.

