Next, participants will have their breath tested (eCO) to assess compliance and physiologic data collection will begin. We will check blood pressure once at the beginning of the session and again at the end. Heart rate will be measured continuously throughout the session.

Approximately five minutes after session onset, participants will sample the session-specific product (4 puffs) followed by a 60-minute rest period. During this time participants will not be allowed to eat or drink outside beverages but we will provide water to drink and they are invited to use their phone, read books/magazines, or watch movies that we provide to them.

After the rest period, participants will complete baseline subjective measures 1 to assess tobacco abstinence symptoms. Immediately after subjective measures 1, two DPTs (session specific DPT, CP-DPT) will be completed. The DPTs take approximately 10 minutes to complete. Then the PRT will begin, which lasts for 30 minutes. Subjective measures 2 begins at 30 minutes post-PRT start. This should take approximately 5 minutes. After this participants will start the 2nd 60-minute rest period.

After the rest period, participants will complete subjective measures 3. This should take about 5 minutes. Then participants will start the CP-PRT, which lasts for 30 minutes. Subjective measures 4 begins at 30 minutes post-CP-PRT start.

When the CP-PRT and Subjectives measures 4 are completed, physio data collection will end and participants will be paid for their time. The study procedures for sessions 1 – 4 should take no more than 220 minutes or 3 hours and 40 minutes.

For the 5th session, participants will experience the same procedures except they will not complete the CP-DPT or CP-PRT. Thus study procedures for the 5th session should take no more than 185 minutes or 3 hours 5 minutes.

Please note there can be some variability in the session times due to participant behavior (i.e., taking shorter/longer than expected to complete measures/tasks).

Session Timeline:

0m – eCO Check; Physiologic data collection begins, additional questions asked.

5m – 4 sample puffs

10m – Begin 60m rest period

70m – Subjectives measure 1

75m – DPTs – 2: session specific DPT, CP-DPT with their own brand cigs

85m – PRT – 30 min

115m – PRT completed; Subjectives measure 2

120m – Begin 60m rest period

180m – Subjectives measure 3

185m – own brand session STOP

OR

185m – CP-PRT – 30 min

215m – CP-PRT completed; Subjectives measure 4

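### In sessions 1–4 the nicotine validation question and Subjective measures 4 follow a task that can pay out own-brand cigarettes, so for participants who smoke them these readings do not isolate the blinded e-cigarette condition

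*Combined protocol and SAP*

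**What the plan says.** All references are to Study Procedures, item 6, unless stated otherwise.

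- **Blinding (Overview).** "The first 4 ECIG conditions will be Latin-square ordered and single blinded such that the participants will not know which condition is administered". Session 5 is always the own-brand cigarette.
- **Validation question (Subjective measures).** "We will also ask a validation question at the end of each session". Participants are asked whether they believe that day's product had nicotine in it. The item refers to a single product and does not name the e-cigarette.
- **Last task in sessions 1–4 (Session Timeline).** "185m – CP-PRT – 30 min". The text after the timeline says that both progressive ratio tasks may yield further puffs of the session e-cigarette or the own-brand cigarette. On delivery, the CP-PRT description says: "Participants will be randomized to either receive the earned cigarette or ECIG puffs first".
- **Fourth subjective assessment (Procedure).** "Subjective measures 4 begins at 30 minutes post-CP-PRT start".
- **Session 5 (Procedure).** "For the 5th session, participants will experience the same procedures except they will not complete the CP-DPT or CP-PRT". Its timeline stops at 185 min, after Subjective measures 3.
- **Analysis (Data analysis).** Subjective data are among the data to be analysed, in general by a mixed ANOVA, with regression or mixed models also allowed. No rule says which subjective time points enter which contrast, and nothing deals with cigarette puffs taken before measure 4 or the question.

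**The concern.** The validation question is the only item in the documents that asks participants whether the product contained nicotine. When it is put to them in sessions 1–4, they may have used two products, one of them a cigarette they know to contain nicotine. In the 0 mg/ml session that cigarette would be the only nicotine received. A *yes* there could refer to the e-cigarette or to the cigarette, and nothing in the quoted wording separates the two.

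This is not noise of equal size in every condition. Study Population, item 3, hypothesizes that willingness to substitute e-cigarettes for cigarettes rises with flux. If so, cigarette puffs in the CP-PRT depend on the condition, and so does the disturbance of whatever is measured next.

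The subjective scales have a similar problem. A cigarette smoked after at least 12 hours of abstinence may relieve withdrawal. If more cigarettes are taken when the e-cigarette is weak, measure 4 is pulled towards no difference between flux conditions. A condition-by-time model using all four assessments would mix this in, and own brand has no value at the fourth time point.

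**Working it through.** **1. Reproduce the timeline.** Step lengths come from the Session Timeline: start-up 5, sample puffs 5, rest 60, Subjective 1 5, purchase tasks 10, PRT 30, Subjective 2 5, rest 60, Subjective 3 5, CP-PRT 30, Subjective 4 5.

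- Sessions 1–4: 5 + 5 + 60 + 5 + 10 + 30 + 5 + 60 + 5 + 30 + 5 = 220 min, the stated length.
- Session 5, without the last two steps: 220 − 30 − 5 = 185 min, as stated.

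**2. Place each assessment against the first possible cigarette puff.** I read the PRT in sessions 1–4 as paying only the session e-cigarette, so own-brand puffs cannot occur before 185 min.

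| Assessment | Sessions 1–4 | Session 5 | Cigarette possible before it in sessions 1–4? |
|---|---|---|---|
| Subjective 1 | 70 min | 70 min | No |
| Subjective 2 | 115 min | 115 min | No |
| Subjective 3 | 180 min | 180 min | No |
| Subjective 4 | 215 min | not done | Yes |
| Validation question | session end, about 220 min | session end, about 185 min | Yes |

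The question therefore comes about 220 − 185 = 35 min later in sessions 1–4. There it falls within about 220 − 215 = 5 min of a task that pays puffs. In session 5 the last such task ended at 115 min, 185 − 115 = 70 min before session end.

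**3. How easily is a cigarette puff reached?** The CP-PRT description sets own-brand requirements of 25, 50, …, 250 presses over ten trials, against a constant 25 presses for each e-cigarette reward.

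- First cigarette puff: 25 presses, the same price as the e-cigarette
- Two puffs: 25 + 50 = 75
- Five puffs: 25 + 50 + 75 + 100 + 125 = 375
- All ten: 25 × (10 × 11 / 2) = 1,375

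Some cigarette use is cheap for an abstinent smoker, but it is not certain. The text caps CP-PRT puffs at 10 without saying whether per product or combined. Either way, cigarette puffs cannot exceed 10.

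**4. Direction of effect on the question (illustration only).** The documents give no rates, so every input here is an assumption. Let p be the share who would say *yes* from the e-cigarette alone, and q the share who say *yes* because of the cigarette.

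Observed *yes* = p + (1 − p) × q

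Assume p = 30% at 0 mg/ml and 80% at 30 mg/ml, a true contrast of 50 points. With a common q the contrast is 50 × (1 − q):

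- q = 0%: 50 points
- q = 25%: 37.5 points
- q = 50%: 25 points
- q = 75%: 12.5 points
- q = 100%: 0 points

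If q is 75% at 0 mg/ml and 25% at 30 mg/ml:

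- 0 mg/ml: 0.30 + 0.70 × 0.75 = 82.5%
- 30 mg/ml: 0.80 + 0.20 × 0.25 = 85.0%
- Contrast: 2.5 points

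The result runs from no loss to complete loss of the contrast. It shows that the disturbance shrinks the contrast, and shrinks it more when cigarette use is concentrated at 0 mg/ml. It does not estimate what happened or will happen in this trial.

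**The case against.** Several stronger readings are tempting, and the documents do not support them.

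- **That these readings fail in every e-cigarette session.** Only participants who took cigarette puffs are affected. For the rest, the question and measure 4 follow the session e-cigarette alone.
- **That Subjective measures 4 is misplaced.** The scales are meant to be given before and after each behavioral measure, so measure 4 is by design the post-CP-PRT reading, and its absence from session 5 follows from that. The gap is only that no rule stops it being pooled as an e-cigarette-condition value. The analysis text commits to no four-point model, so that harm is possible rather than planned.
- **That end-of-session blood pressure has the same defect.** The plan states "We will check blood pressure once at the beginning of the session and again at the end", and it describes physiological measures as primarily for safety. A reading after all exposure serves that purpose, and heart rate is recorded continuously. I make no criticism of it.
- **That the main results are biased.** The primary measures are the four choice tasks. In sessions 1–4 both purchase tasks and the PRT finish before any own-brand puff, and in the CP-PRT the cigarette choice is the outcome.
- **That a formal test of the blind is undermined.** The plan calls the item a validation question and ties no analysis or decision to it. The uploaded subjective-measures form is not among the documents and may explain which product is meant.

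There is also a fair objection to moving the question before the CP-PRT: it could cue participants about nicotine just before a primary choice task. That stands, and it is why rewording comes first below. Rewording, for its part, settles which product is meant but cannot remove any carry-over of nicotine effects from a cigarette just smoked.

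**Conclusion.** The concern holds in a limited form. As written, the validation question and Subjective measures 4 in sessions 1–4 can follow own-brand smoking whose amount is expected to depend on flux. For participants who smoked, these readings do not isolate the blinded e-cigarette condition, and the problem is greatest at 0 mg/ml. They are also not matched to session 5.

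The extent is one of four subjective time points and one secondary item, after 0 to 10 cigarette puffs. The numerical size of the bias is unknown. The conclusion on sequence rests on the protocol's timeline and on two readings of its text: that end of session means after the last task, and that earned CP-PRT puffs are taken as part of that task. The exact minutes of the question and of smoking are not given. The expectation that the disturbance differs by condition rests on the protocol's own substitution hypothesis. The point is worth acting on because the remedy is nearly free.

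**What to change.** 1. Reword the question to name the session product: *the e-cigarette you used today* in sessions 1–4, and the cigarette in session 5. Report the answers by condition alongside the number of cigarette puffs taken in the CP-PRT.
2. As an alternative, ask it before the CP-PRT, with Subjective measures 2 or 3, in all five sessions. This matches timing and leaves only one product used, but the investigators must accept a small risk of cueing participants before the CP-PRT.
3. Add to Data analysis that flux and own-brand contrasts of the subjective scales use measures 1–3, and that measure 4 is reported only as a post-choice, mixed-product value.

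The cost is a wording change to one REDCap item, with amendment of the approved form, and a few sentences of analysis text. No visits are added and sessions need not be longer. Sessions already run keep the old item and are reported separately. That leaves mixed versions within any participant who is partway through the crossover, a reason to settle the change once. If data collection is over, the puff-count reporting in step 1 and all of step 3 can still be applied.
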